10.1 Assessment and Reporting of Adverse Events

To monitor subject safety throughout this study, any procedure or device related adverse events will be recorded. Information on all adverse events will be maintained by event type. The investigator will complete an Adverse Event form if any adverse event is reported or observed for a subject during this study, even if the event was acknowledged as a risk factor in the Informed Consent form.

Adverse device effects refer to any undesirable clinical or medical occurrence associated with use of the device or participation in the study. Any/all adverse device effects are to be recorded via the Adverse Event form. Adverse device effects will be reported if observed, even if they were acknowledged as risk factors in the Informed Consent form.

10.2 Unanticipated Adverse Device Effects

Unanticipated adverse device effects refer to any event not identified above that represents a “serious adverse effect on health or safety or any life-threatening problem or death caused by, or associated with, a device if that effect, problem or death was not previously identified in nature, severity, or degree of incidence in the investigational plan or application, or any other unanticipated serious problem associated with a device that relates to the rights, safety, or welfare of subjects.” [FDA 21 CFR 812.3(s)]

Investigators are to inform their respective Institutional Review Boards (IRBs) and Cochlear Americas immediately if an unanticipated adverse device effect is suspected (no more than 10 working days after the investigator learns of the effect). If the case is determined to be an unanticipated adverse device effect, the investigator will fill out an “Unanticipated Adverse Device Effect Form.” Cochlear Americas will report the results of an evaluation of the unanticipated adverse device effect to all reviewing IRBs and investigators within 10 working days after first receiving notice of the event.

CONFIDENTIAL

Version 1.0 Usability of the CP950 sound processor with experienced cochlear implant users.

11. Study Completion

11.1 Completed Subjects

Once the 1 month post-fitting visit is completed, the subject will be deemed complete. Each subject will be required to return the CP950 Sound Processor to the providing clinic. Subjects will continue to receive standard clinical follow-up care at their cochlear implant facility after the study.

11.2 Discontinued Subjects

Any subject may voluntarily discontinue the study at any time without prejudice. The Investigator may discontinue a subject from the study at any time if (s)he considers that remaining in the study compromises the subject's health or the subject is not sufficiently cooperative. In either event, reason(s) for discontinuation should be recorded on a study withdrawal form, provided as part of the CRFs for the study. Possible reasons for study discontinuation include the following:

- AE necessitating discontinuation from the study
- The subject is lost to follow-up
- Voluntary decision to withdraw consent made by the subject
- Investigator decision
- Other reason

In case of a subject lost-to-follow-up, the Investigator must attempt to contact the subject (or relative/family contact) by phone, email or letter at least three times. If attempts are unsuccessful, the 'subject withdrawal' form is to be completed in the study file and reported, as appropriate, in required reports to the Sponsor and IRB.

11.3 Premature Study Termination

The Sponsor may terminate the study early in the case of major non-adherence to the protocol, or if it is anticipated that recruitment will not be met for the required number of subjects to complete the study objectives. In the event of premature study termination, the subjects who are already enrolled will be sponsored through study completion.

12. Data Analysis

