11.3 Premature Study Termination	14
12. Data Analysis	14

CONFIDENTIAL

Version 1.0 Usability of the CP950 sound processor with experienced cochlear implant users.

12.1	Statistical Analysis	14
12.2	Sample Size.....	15
13.	Risk Benefit Statement	15
13.1	Benefits	15
13.2	Risks	15
14.	Good Clinical Practices Statement	15
15.	Access to Study Documents and Study Monitoring	15
16.	Quality Control and Assurance	15
17.	Institutional Review Board	16
18.	Informed Consent Process	16
19.	Confidentiality.....	16
20.	Protocol Deviations and Amendments.....	16
21.	Data Management.....	16
22.	Record Keeping and Retention.....	17
23.	Study Report and Publication	17

CONFIDENTIAL

Version 1.0 Usability of the CP950 sound processor with experienced cochlear implant users.

1. Clinical Investigation Synopsis

Investigation title	Usability of the CP950 sound processor with experienced cochlear implant users.
Name of investigational device	CP950 Sound processor CP950 Programming Cable Adaptor Cochlear Wireless Programming Pod
Total expected duration of the clinical investigation	6 months
Enrollment period	3 months
Expected duration per subject	1 Month post CP950 Fitting
Investigational design	Single-subject usability study
Number of subjects	Up to 30 subjects
Number of investigational sites	Up to 3 sites
Inclusion criteria	
 1. At least 6 months experience with a Nucleus 24 series or later implant in at least one implanted ear 2. Subjects age 12 and older who are cognitively and developmentally able to complete all study related questionnaires as deemed by the principal investigator or delegated staff 3. At least 3 months experience with the CP810, CP920 or CP910 sound processor 4. Ability to use 2 zinc air batteries with their current MAP 5. Willingness to participate in and to comply with all requirements of the protocol for the duration of the trial
Exclusion criteria	
 1. Unrealistic expectations on the part of the subject, regarding the possible benefits, risks and limitations that are inherent to the procedure and prosthetic device 2. Additional disabilities that would prevent participation in evaluations 3. Implant types not currently supported by the

CONFIDENTIAL

Version 1.0 Usability of the CP950 sound processor with experienced cochlear implant users.

	CP950 sound processor (i.e.,N22)																		

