9.2 Visit Schedule & Procedures

9.2.1 Visit 1:

The following activities will occur during Visit 1:

- 1) Subjects will be converted from their current behind the ear sound processor (CP810 or CP900 series) to the CP950 sound processor using the recommended clinical conversation parameters. An anonymous .cdx file will be sent to the Sponsor.
- 2) The Sound Processor MAP conversion will be completed using the Wireless Pod and Custom Sound version 4.
- 3) If applicable, the subjects' wireless accessories will be paired to the CP950 Sound Processor.
- 4) The subject will be instructed to utilize the CP950 Sound Processor, Remote Assistant or Control and wireless accessories for a minimum of 30 days +/-1 week.
- 5) The subject will complete a weekly diary documenting the CP950 Sound Processor user experience.

9.2.2 Visit 2:

The following activities will occur during Visit 2:

- 1) Datalogging for the CP950 Sound Processor will be extracted. An Anonymous .cdx file will be sent to the Sponsor.
- 2) The CP950 Take Home Use Questionnaire will be completed by the subject.
- 3) The CP950 Sound Processor will be collected from each subject.

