12.2 Sample Size

The proposed study is designed to collect usability data on up to 30 subjects across up to 3 participating sites. Since the study was designed with the intent to collect usability data, not for the purposes of demonstrating safety and efficacy, formal sample size and power analyses have not been completed. The study is intended to provide clinical guidance and regional experience on the fitting and use associated with CP950 Sound Processor on existing cochlear implant recipients. Based on a sample size of 30 subjects, there is an approximately 80% probability of observing one or more major usability issues for issues that occur in the population at a rate of as low as 5.4%.

Subject enrollment is estimated to take 3 months to recruit up to 30 subjects across 3 sites. The enrollment period may be extended if required.

13. Risk Benefit Statement

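### Does the early-termination clause in Section 11.3 fail because the protocol never defines the required number of subjects?

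*Protocol*

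**What the plan says.** Section 11.3 gives two grounds on which the sponsor may stop early. The first reads "The Sponsor may terminate the study early in the case of major non-adherence to the protocol"; the second is "if it is anticipated that recruitment will not be met for the required number of subjects to complete the study objectives". The same section adds that subjects already enrolled will be supported through to completion.

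The size of the study appears in two places. The synopsis gives "Up to 30 subjects". Section 12.2 says "The proposed study is designed to collect usability data on up to 30 subjects across up to 3 participating sites", and repeats the ceiling when it estimates three months for enrolment, a period that may be extended. It explains that "formal sample size and power analyses have not been completed" because the aim is usability data and not a demonstration of safety and efficacy. It then describes what the full sample would deliver: "Based on a sample size of 30 subjects, there is an approximately 80% probability of observing one or more major usability issues", for issues with a population rate as low as 5.4%.

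On the analysis, Section 12.1 plans individual tabulation and group descriptive statistics only. The primary instrument is given at the second visit (Section 9.2.2): "The CP950 Take Home Use Questionnaire will be completed by the subject".

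**The concern.** Section 11.3 speaks of a required number as though it were fixed elsewhere, and it is not. A maximum cannot serve, because any recruitment total satisfies it. If 30 is taken as the requirement, the wording in the synopsis and Section 12.2 that makes 30 a ceiling looks wrong. Slow recruitment also has two opposite permitted responses, stopping under Section 11.3 or extending enrolment under Section 12.2, with no number to choose between them.

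The unit of counting is a second loose end. Section 11.3 is about recruitment, but the objectives are met by questionnaires completed at the second visit, and Section 11.2 foresees withdrawals and loss to follow-up. If the number matters, one would want to know whether it counts subjects enrolled or subjects with data.

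At stake would be the detection statement in Section 12.2. With no floor, the study could end at any size up to 30 and still comply with the text, while the 80% figure holds only near the cap.

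**Working it through.** **Inputs.** Sample size 30, issue rate 5.4% and detection probability of about 80%, all from Section 12.2. The protocol gives no minimum size and no attrition rate, so every size below 30 used here is an illustration.

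**Step 1: reproduce the plan's figure.** The probability that at least one of n subjects has an issue with rate p is 1 − (1 − p)^n. With n = 30 and p = 0.054 this is 1 − 0.946^30 = 0.811. The stated figure of approximately 80% is correct.

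**Step 2: the smallest size that supports it.** n = ln(0.2) / ln(0.946) = 28.99, so 29 subjects give 80.0%. At 30 subjects, the rate seen with exactly 80% probability is 1 − 0.2^(1/30) = 5.2%.

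**Step 3: what smaller samples would give.**

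| Subjects | Probability of at least one occurrence at 5.4% | Rate seen with 80% probability |
|---|---|---|
| 30 | 81.1% | 5.2% |
| 29 | 80.0% | 5.4% |
| 27 | 77.7% | 5.8% |
| 24 | 73.6% | 6.5% |
| 20 | 67.1% | 7.7% |
| 10 | 42.6% | 14.9% |

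The loss is gradual. Three subjects short of the cap costs 81.1 − 77.7 = 3.4 percentage points. A serious fall needs a sample far below the plan.

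**Step 4: set the sections side by side.**

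- *Is it a contradiction?* A ceiling of 30 and an unstated minimum can both hold. The termination ground becomes impossible to meet only if the ceiling is put in place of the required number, and no section does that. As written, the sponsor judges whether recruitment will suffice for the objectives, and recruitment that stalls after a few subjects would plainly qualify.
- *Does the clause bind anyone?* No. The sponsor may act, and the ground is an anticipated shortfall. If 29 were written in, the sponsor could still continue below it, and could still stop on a forecast. Most of the discretion would remain.
- *Could stopping distort the analysis?* The ground looks at recruitment and not at questionnaire results. Section 12.1 contains no hypothesis test, error rate or success threshold.
- *Does the detection statement overclaim?* It opens "Based on a sample size of 30 subjects", so it is conditional on that size and promises nothing for smaller ones. With data tabulated by subject, the achieved number will be visible and the formula in Step 1 gives the corresponding probability.
- *Which subjects count?* Section 12.2 first ties its 30 to subjects on whom usability data are collected. Its later sentence on recruitment is looser. Usability problems can also surface before the second visit, through pairing at the first visit, the weekly diary (Section 9.2.1) and adverse event forms (Section 10.1), so a subject without a final questionnaire is not necessarily lost to the detection of issues.

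**The case for a change.** The best case for a change is that the termination criterion and the sample size both stand in this protocol, so the gap cannot be left to a separate analysis plan, and closing it costs almost nothing: one number in Section 12.2 with a cross-reference, or deletion of the recruitment ground. Reading 30 as the implied requirement is only an inference, because Section 12.2 says what 30 subjects would yield and never calls 30 required. A study report could not say whether the number in Section 11.3 had been reached.

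The textual part of this stands. The number is undefined, and 30 is an implied planning size at most. The consequence does not stand. The protocol does not ask the report to say whether a required number was reached, and no conclusion rests on it.

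The remedies also bring little. A floor of 29 completed questionnaires under a cap of 30 fails with the second loss. A floor of 27 introduces a figure the protocol never uses. Either floor would mix a count of completers with a clause about recruitment. Deleting the ground takes away a sponsor's right in order to tidy a phrase.

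**Conclusion.** The concern is right on the wording: Section 11.3 refers to a number that the protocol does not set. It does not amount to a defect that needs a change. The clause is administrative and discretionary, enrolled subjects are carried through, the analysis is descriptive, and the only quantitative claim linked to the sample size is correct as stated (81.1% for 30 subjects at a 5.4% rate) and explicitly conditional on 30.

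The worst plausible effect is a smaller descriptive study with a lower chance of revealing an uncommon problem: 77.7% at 27 subjects, 67.1% at 20. Those sizes are illustrations, since the protocol predicts no shortfall. A sensible reader will take 30 as the planning size and judge any shortfall against it, so naming that size in Section 11.3, or dropping the word for a requirement, would be copy-editing with no effect on data, analysis or subjects.

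This conclusion rests on the study remaining descriptive. If a success criterion or a formal comparison were attached to the questionnaire, a stated minimum would matter.

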12.1 Statistical Analysis

All subjects who are consented into the clinical study will constitute the intention-to-treat (ITT) population for the purposes of safety evaluation. Only subjects fit with the CP950 Sound Processor and completed per the protocol will be considered as the completed cases (CC) population and per protocol (PP).

Demographic and outcomes data will be tabulated individually along with group summary descriptive statistics.

Descriptive statistics will be summarized for the following assessments:

- CP950 Take Home Questionnaire for existing cochlear implant users
- The number of connections as well as the success or failure of those connections to both the Wireless Pod and Wireless Accessories will be captured

CONFIDENTIAL

Version 1.0 Usability of the CP950 sound processor with experienced cochlear implant users.

- Field use data such as Time on Air, Listening Environment, Program Usage, and Accessory Use

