13.2 Risks

With any cochlear implant mapping, there is a very small risk of unintentional over-stimulation. Subjects may experience sounds during mapping that are uncomfortably loud. Mitigation of this risk is similar to that used during clinical cochlear implant mapping wherein the sound processor is removed from the subjects head and/or the stimulation to the sound processor is ceased in Custom Sound.

There is risk that the CP950 Sound Processor will not connect wirelessly to the Wireless Pod. If this occurs, CP950 Sound Processor programming will occur using the traditional programming cable.

14. Good Clinical Practices Statement

The study obligations for the Investigator(s) are outlined in guidelines for Good Clinical Practice (GCP), ISO14155:2011 (Clinical Investigation of Medical Devices for Human Subjects – Good Clinical Practice), and the Declaration of Helsinki.

15. Access to Study Documents and Study Monitoring

Investigator(s) will provide access to study documentation including source data for the purposes of monitoring, audits, IRB review, and regulatory inspections.

16. Quality Control and Assurance

Study sites may be subject to Quality audits at any point during the study. Regulatory agencies may conduct inspections during the course of the clinical investigation and after study completion.

CONFIDENTIAL

Version 1.0 Usability of the CP950 sound processor with experienced cochlear implant users.

17. Institutional Review Board

Each site will obtain approval from its designated IRB prior to commencing any study-related activities. A copy of the IRB approval will be kept in the Investigator file(s). Any additional requirements imposed by the IRB and/or regulatory authority shall be followed. The Investigator(s) will submit the appropriate documentation if any necessary extension or renewal of the IRB approval must be obtained.

18. Informed Consent Process

Written informed consent shall be obtained from each subject after explaining the rationale for and the details, aims, and objectives of the study, the risks and benefits of the trial treatment (and alternative treatments), and the extent of the patient's involvement. The Investigator is responsible for ensuring that all patients give written informed consent prior to any study-related examination or activity. All patients shall sign and date the Informed Consent Form, and a copy of the Informed Consent Form shall be given to the patient.

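### Does defining the safety set by consent leave subjects exposed to the CP950 out of the safety evaluation?

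*Protocol*

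**What the plan says.** Protocol section 12.1 defines two sets under three labels. For safety: "All subjects who are consented into the clinical study will constitute the intention-to-treat (ITT) population for the purposes of safety evaluation". For the other set: "Only subjects fit with the CP950 Sound Processor and completed per the protocol will be considered as the completed cases (CC) population"; the same definition also carries the per-protocol label.

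Four other places bear on the point:

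- Section 18 (Informed Consent Process) requires that "all patients give written informed consent prior to any study-related examination or activity".
- Section 10.1 gives a broad definition: "Adverse device effects refer to any undesirable clinical or medical occurrence associated with use of the device or participation in the study". The adverse event definition that opens section 10 likewise covers device, procedure and participation.
- Section 11.2 lists, among the possible reasons for leaving early, "AE necessitating discontinuation from the study".
- Section 12.2 says the study was designed to collect usability data, "not for the purposes of demonstrating safety and efficacy".

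**The concern.** A device safety summary is normally read per exposed subject. Here exposure starts with fitting, yet neither set in section 12.1 consists of the fitted subjects and only those. The consented set can include someone who signs and is then found ineligible or withdraws before fitting. That person cannot have a device event but still counts in the denominator. The completer set has the opposite fault: a fitted subject who stops because of an adverse event drops out of it, so membership depends on the outcome being counted.

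If safety were reported as a percentage, both sets could make the device look better than it is. The consented set would do so by dilution, and the completer set by removing the affected subjects. In a study of up to 30 subjects, a few people can move a percentage visibly.

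**Working it through.** **1. Is any exposed subject missing from the safety set?** Completion requires the visit one month after fitting (section 11.1), so completed subjects are a subset of fitted subjects. Section 18 puts consent before any study activity, so fitted subjects are a subset of consented subjects:

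completed ⊆ fitted ⊆ consented.

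The safety set is the outermost of the three. It contains every subject exposed to the CP950, including those who stop early for an adverse event.

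**2. Does the safety set match what is to be recorded?** Sections 10 and 10.1 include events associated with taking part in the study, and these can occur after consent and before fitting. A fitted-only set would leave them out. The consented set takes in every event that the definitions cover.

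**3. Is safety ever analysed on the completers?** Section 12.1 assigns safety evaluation to the consented set and nowhere to the completer set. The bias from removing early stoppers would arise only if the analyst departed from the text.

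**4. Is there a planned percentage to distort?** Section 12.1 lists descriptive summaries for the questionnaire, the wireless connections and the field use data. None is an adverse event rate. Section 10.1 says event information is kept by event type, and section 12.1 has outcomes tabulated subject by subject. The one probability in the plan, about 80% in section 12.2, concerns usability issues: 1 − (1 − 0.054)^30 = 0.811. It reproduces, and it does not depend on the safety set.

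**5. How large could dilution be if someone computed a rate anyway?** Assume 30 consented, of whom u are never fitted. The protocol gives no value for u, so a range is shown. With k subjects having device events, the ratio of the rate per consented subject to the rate per fitted subject is

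(k/30) ÷ (k/(30 − u)) = (30 − u)/30.

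| Never fitted (u) | Ratio | k = 3, per consented | k = 3, per fitted |
|---|---|---|---|
| 0 | 1.00 | 3/30 = 10.0% | 3/30 = 10.0% |
| 1 | 0.97 | 10.0% | 3/29 = 10.3% |
| 2 | 0.93 | 10.0% | 3/28 = 10.7% |
| 3 | 0.90 | 10.0% | 3/27 = 11.1% |
| 5 | 0.83 | 10.0% | 3/25 = 12.0% |

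The exact (Clopper–Pearson) 95% interval for 3/30 is 2.1% to 26.5%, far wider than any shift in the table. The schedule in section 9.3 puts enrolment, consent and fitting at the same Visit 1. Section 13.2 provides for cable programming if the wireless connection fails. Both make a small u plausible, though neither guarantees zero.

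**The case for a change.** The strongest case is that the protocol itself ties safety to consent, so this is more than a detail left open for the analysis plan. Eligibility checks specific to the study must follow consent. The synopsis, for example, requires that the current MAP can run on two zinc air batteries. A subject can therefore be consented and never fitted. The study is also meant to guide fitting and use of the device, for which a count per fitted subject would be informative. And if the completer set were used instead, an event subject who stopped would vanish: with 3 event subjects, 1 of them stopping and all other fitted subjects completing, the figure would be 2/29 = 6.9%, 2/28 = 7.1% or 2/26 = 7.7% for u = 0, 1 or 3.

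It stands that no set in section 12.1 is exactly the fitted subjects, and the arithmetic is right under its assumptions. But the completer percentages measure a use of that set which the plan does not make. The consented set excludes no one who was exposed. Whether a subject was fitted must be known anyway to apply the completer definition, so the number fitted can be counted. An analysis plan that added a fitted-only denominator beside the consented set would not contradict section 12.1.

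**Conclusion.** The concern does not hold. The safety set contains all exposed subjects, agrees with the protocol's own adverse event definitions and loses no event. Following section 12.1 as written gives a sound descriptive account of safety. Possible dilution is nil if every consented subject is fitted. With 3 of 30 unfitted it is about one percentage point on a 10% figure, and the protocol plans no such figure.

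This rests on consent being obtained before fitting, as section 18 requires, and on safety being evaluated on the consented set, as section 12.1 says. The numbers unfitted are illustrative. A separate as-fitted denominator would be a reasonable addition to the tables, but its absence from the protocol is no error.
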